**After the preceding procedures and assessments are completed:**

- Study drug administration (record date and time of dose of study drug) ([Section 9](#))
- Vital sign measurements (sitting blood pressure, heart rate, respiratory rate, oral temperature) will be performed at 15, 30, and 45 minutes after the start of the infusion and at completion of the infusion ([Section 6.5](#))
- Pulse oximetry will be measured at 15, 30, and 45 minutes after the start of the infusion and at completion of the infusion ([Section 6.5](#))
- Concomitant medication assessment ([Section 6.9](#))
- AE assessment ([Section 6.10](#))

**After administration of study drug, the following post treatment procedures and assessments will be performed:**

- Vital sign measurements (sitting blood pressure, heart rate, respiratory rate, oral temperature): 30 minutes, 1 hour and 2 hours following completion of the infusion; abnormal results to be repeated after 5 minutes of rest ([Section 6.5](#))
- Pulse oximetry: 30 minutes, 1 hour and 2 hours following completion of the infusion ([Section 6.5](#))
- PK sample collection at 5 minutes and 2, 4, 6 hours after the end-of-study drug infusion; record collection date and time for each PK sample ([Section 6.7](#))
- 12-Lead ECG (to be obtained in triplicate at 5 minutes after the completion of study drug infusion ([Section 6.6](#)))
- Concomitant medication assessment ([Section 6.9](#))
- AE assessment ([Section 6.10](#))

**7.12 Follow-up Day 29**

On Day 29 (24 hours  $\pm$  1 hour from end-of-infusion time on Day 28), the subject will return to the clinic and the following procedures are to be performed:

- Vital sign measurements (after 5 minutes of rest; sitting blood pressure, heart rate, respiratory rate, oral temperature); abnormal results to be repeated after 5 minutes of rest ([Section 6.5](#))
- PD sample collection ([Section 6.7](#))
  - IgG, IgG subtypes (IgG1-4), IgA, IgM
- PK sampling (record collection date and time) ([Section 6.7](#))
- Concomitant medication assessment ([Section 6.9](#))
- AE assessment ([Section 6.10](#))

### 7.13 Follow-up Day 30

On Day 30 (48 hours  $\pm$  2 hours from end-of-infusion time on Day 28), the subject will return to the clinic and the following procedures are to be performed:

- Vital sign measurements (after 5 minutes of rest; sitting blood pressure, heart rate, respiratory rate, oral temperature); abnormal results to be repeated after 5 minutes of rest (Section 6.5)
- PD sample collection (Section 6.7)
  - IgG, IgG subtypes (IgG1-4), IgA, IgM
- PK sampling (record collection date and time) (Section 6.7)
- Concomitant medication assessment (Section 6.9)
- AE assessment (Section 6.10)

### 7.14 Follow-up Day 33

On Day 33 (120 hours  $\pm$  4 hours from end-of-infusion time on Day 28), subjects will return to the clinic and the following procedures are to be performed:

- Vital sign measurements (after 5 minutes of rest; sitting blood pressure, heart rate, respiratory rate, oral temperature); abnormal results to be repeated after 5 minutes of rest (Section 6.5)
- Clinical safety laboratory tests (hematology, serum chemistry panel, urinalysis) (Section 6.7)
- PDAI Score (Section 6.4)
- PK sampling (record collection date and time) (Section 6.7)
- PD sample collection (Section 6.7)
  - IgG, IgG subtypes (IgG1-4), IgA, IgM
  - CIC
  - Anti-Dsg (1 and 3) antibody titer
  - C3
  - AECA
  - RNAseq
  - Urine IgG
  - Exploratory pemphigus immune response biomarkers
- Optional skin biopsy (Section 6.12)
- Photography (Section 6.11)
- Concomitant medication assessment (Section 6.9)
- AE assessment (Section 6.10)

### 7.15 Follow-up Day 42

On Day 42 ( $\pm 3$  days), subjects will return to the clinic and the following procedures are to be performed:

- Complete physical exam ([Section 6.3](#))
- Vital sign measurements (after 5 minutes of rest; sitting blood pressure, heart rate, respiratory rate, oral temperature); abnormal results to be repeated after 5 minutes of rest ([Section 6.5](#))
- Clinical safety laboratory tests (hematology, serum chemistry panel, urinalysis) ([Section 6.7](#))
- PDAI Score ([Section 6.4](#))
- PD sample collection ([Section 6.7](#))
  - IgG, IgG subtypes (IgG1-4), IgA, IgM
  - CIC
  - Exploratory pemphigus immune response biomarkers
- Concomitant medication assessment ([Section 6.9](#))
- AE assessment ([Section 6.10](#))

### 7.16 Follow-up Day 56

On Day 56 ( $\pm 5$  days), subjects are to return to the clinic and the following procedures are to be performed:

- Complete physical exam ([Section 6.3](#))
- Vital sign measurements (after 5 minutes of rest; sitting blood pressure, heart rate, respiratory rate, oral temperature); abnormal results to be repeated after 5 minutes of rest ([Section 6.5](#))
- Clinical safety laboratory tests (hematology, serum chemistry panel, urinalysis) ([Section 6.7](#))
- Pregnancy test ([Section 6.7](#))
- 12-Lead ECG (to be obtained in triplicate after 5 minutes of rest in the sitting position) ([Section 6.6](#))
- Serum tetanus antibody and VZV antibody; Testing at Day 56 will not be done for any subject whose baseline titer is below the level of detection. See [Section 6.7.3](#) for additional information.
- Immunogenicity sample collection ([Section 6.7](#))
- PDAI Score ([Section 6.4](#))
- PD sample collection ([Section 6.7](#))
  - IgG, IgG subtypes (IgG1-4), IgA, IgM
  - CIC

- Anti-Dsg (1 and 3) antibody titer
- C3
- AECA
- RNAseq
- Urine IgG
- Immune phenotyping
- Exploratory pemphigus immune response biomarkers
- Optional skin biopsy ([Section 6.12](#))
- Photography ([Section 6.11](#))
- Concomitant medication assessment ([Section 6.9](#))
- AE assessment ([Section 6.10](#))

### 7.17 Follow-up Day 84

On Day 84 ( $\pm 5$  days), subjects are to return to the clinic and the following procedures are to be performed:

- Complete physical exam ([Section 6.3](#))
- Vital sign measurements (after 5 minutes of rest; sitting blood pressure, heart rate, respiratory rate, oral temperature); abnormal results to be repeated after 5 minutes of rest ([Section 6.5](#))
- Clinical safety laboratory tests (hematology, serum chemistry panel, urinalysis) ([Section 6.7](#))
- Serum tetanus antibody and VZV antibody testing if required. See [Section 6.7.3](#) for additional information.
- Immunogenicity sample collection ([Section 6.7](#))
- PDAI Score ([Section 6.4](#))
- PD sample collection ([Section 6.7](#))
  - IgG, IgG subtypes (IgG1-4), IgA, IgM
  - CIC
  - Anti-Dsg (1 and 3) antibody titer
  - C3
  - AECA
  - RNAseq
  - Urine IgG
  - Exploratory pemphigus immune response biomarkers
- Optional skin biopsy ([Section 6.12](#))
- Photography ([Section 6.11](#))
- Concomitant medication assessment ([Section 6.9](#))
- AE assessment ([Section 6.10](#))

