- b: **Vital sign** measurements (sitting blood pressure, heart rate, respiratory rate, and oral temperature) to be obtained after 5 minutes of seated rest. Any abnormal measurements are to be repeated after 5 minutes of rest. On Days 0, 7, 14, 21, and 28 vital sign measurements will be collected immediately prior to the infusion; 15, 30, and 45 minutes after the start of the infusion; at completion of the infusion; and 30 minutes, 1 hour and 2 hours following completion of the infusion.
- c: **Pulse oximetry**: On Days 0, 7, 14, 21, and 28, pulse oximetry to be measured immediately prior to the infusion; 15, 30, and 45 minutes after the start of the infusion; at completion of the infusion; and 30 minutes, 1 hour and 2 hours following completion of the infusion.
- d: **Clinical safety labs**: hematology, clinical chemistry, and urinalysis (see [Section 6.7](#) for a complete list). Full clinical safety lab draws will be collected at Screening and on Days 0, 7, 14, 21, 28, 33, 42, 56, 84 and 112.
- e: **Pregnancy test**: To be performed at time of screening and prior to first dose of SYNT001 on Day 0 and on Days 56 and 112 (urine or serum test is acceptable, however, positive urine tests must be confirmed with serum testing.)
- f: Digital 12-lead **ECG** to be obtained after 5 minutes of rest in the supine position and in triplicate at least 1-2 minutes apart (see [Section 6.6](#) for additional information). On Days 0 and 28 to be obtained 5 minutes after the completion of infusion. Day 12 ECG will be collected only if the visit is conducted at the study site.
- g: **Serology**: Testing at Day 56 will not be done for any subject whose baseline titer is below the level of detection. If the Day 56 results are greater than 30% below the baseline value, or if the subject falls below the level of detection, the subject will be re-tested at Day 84; if still below the baseline value (or level of detection), the subject will be re-tested at Day 112. Any subject whose baseline value for tetanus or VZV was above the detectable level at baseline, and is not within 30% of the baseline value or is below the detectable level by Day 112, will be referred to their primary care physician for further management. See [Section 6.7.3](#) for additional information.

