## 6.6 12-Lead Electrocardiogram (ECG)

Digital 12-lead ECG measurements will be obtained at screening, on Days 0 and 28 at 5 minutes after the completion of the infusion and at the Day 56 visit. Subjects who conduct their Day 12 visit at the investigative site, as opposed to an at-home nurse visit, will have an additional ECG performed. ECGs are to be performed with the subject in a supine position having rested in this position for at least 5 minutes before each reading. ECGs are to be performed in triplicate, each 1 to 2 minutes apart. See [Table 2](#) for timing window allowances with respect to performing ECG.

The following ECG parameters will be collected: PR interval, QRS interval, and QT interval. The ECG findings will be evaluated by a qualified physician for the presence of abnormalities (qualitative assessment). The physician will assess each ECG as normal, abnormal/not clinically significant, or abnormal/clinically significant.

Normal QTcF is  $\leq 450$  msec.

Abnormalities in the ECG that appear following therapy or that result in clinical signs and symptoms are considered clinically significant for the purposes of this study and will be recorded on the AE eCRF.

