## 7 STUDY ASSESSMENTS

### 7.1 Screening Period: Day -14 to Day -1

Informed consent must be obtained before any study-specific samples are taken or study-specific tests or evaluations are conducted. The following assessments at the screening visit are to occur within 14 days before dosing. Study eligibility will be based on satisfying all the study inclusion and exclusion criteria.

At the screening visit, information will be collected and subjects will have clinical evaluations as follows:

- Informed consent ([Section 6.1](#))
- Medical history and demographic data ([Section 6.2](#))
- Review inclusion and exclusion criteria ([Section 5.2](#), [Section 5.3](#))
- Complete PE, including height and weight ([Section 6.3](#))
- Vital sign measurements (after 5 minutes of rest; sitting blood pressure, heart rate, respiratory rate, oral temperature); abnormal results to be repeated after 5 minutes of rest ([Section 6.5](#))
- 12-Lead ECG (to be obtained in triplicate after 5 minutes of rest in the supine position) ([Section 6.6](#))
- Clinical safety laboratory tests (hematology, serum chemistry panel, urinalysis) ([Section 6.7](#))
- Pregnancy test ([Section 6.7](#))
- Hepatitis and HIV screen ([Section 6.7](#))
- PD sample collection ([Section 6.7](#))
  - IgG, IgG subtypes (IgG1-4), IgA, IgM
  - Anti-Dsg (1 and 3) antibody titer
- Concomitant medication assessment ([Section 6.9](#))
- AE assessment ([Section 6.10](#))

### 7.2 Enrollment and First Treatment: Day 0

Study Day 0 is defined as the date the subject is administered their first dose of study drug. On Day 0, subjects will be asked to come to the clinic and the following procedures will be performed prior to the first dose of study drug:

- Complete physical exam ([Section 6.3](#))
- Vital sign measurements (sitting blood pressure, heart rate, respiratory rate, oral temperature); to be measured immediately prior to the infusion ([Section 6.5](#))
- Pulse oximetry (to be measured immediately prior to the infusion) ([Section 6.5](#))

- 
- Clinical safety laboratory tests (hematology, serum chemistry panel, urinalysis) ([Section 6.7](#))
  - Pregnancy test (Section 6.7)
  - Serum tetanus antibody and VZV antibody (Section 6.7)
  - PDAI Score ([Section 6.4](#))
  - PK baseline sample collection (collected just prior to the start of the study drug infusion) (Section 6.7)
  - Immunogenicity sample collection (collected just prior to the start of study drug infusion) (Section 6.7)

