## **12.5 Safety Data**

Safety observations and measurements include AEs, safety laboratory tests, vital sign measurements, PEs, and ECGs.

Treatment-emergent AEs will be summarized using the Medical Dictionary for Regulatory Activities (MedDRA®; Version 19 or higher) System Organ Class (SOC) and preferred term, classified from verbatim terms. The incidence and percentage of subjects with at least 1 occurrence of a preferred term will be included, using the most severe grade. The number of events per preferred term will also be summarized. Causality (relationship to study treatment) will be summarized separately.

AEs, SAEs, and AEs leading to withdrawal, dose modification, or treatment discontinuation will be listed by subject, cohort, and overall per SOC and preferred terms. Duration of AEs will be determined and included in listings, along with action taken and outcome.

Laboratory results will be summarized by cohort. Incidence of laboratory abnormalities will be summarized. The worst on-study grade after the first dose of study drug will be summarized. Results for variables that are not coded will be presented in the listings as below, within, and above the normal limits of the local laboratory.

Vital sign measurements and change from baseline will be summarized at each scheduled time point by cohort using descriptive statistics.

Arithmetic mean of parameters from triplicate ECG will be calculated first for each participant at each planned time point. Then summary statistics of ECG test parameters (mean of triplicate) and change from baseline to each post-dose time point will be calculated. Shift tables for ECG test result category change (normal, abnormal, clinically abnormal) from pre-dose to each post-dose time point showing number and percentage of subjects with movement between categories will be presented by treatment group. Frequency and percentage of subjects experiencing potential QTc prolongation ( $QTcF > 450$ ) will be summarized at each time point by cohort.

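### Section 7.16 has the Day 56 ECG taken sitting, against the supine rule in Section 6.6 and Table 1, so the last ECG may not be comparable with the supine screening ECG

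*Protocol*

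**What the plan says.** The protocol gives ECG posture in four places.

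- Section 6.6 sets the general rule: "ECGs are to be performed with the subject in a supine position having rested in this position" before each reading. The ECGs it covers are screening, those "on Days 0 and 28 at 5 minutes after the completion of the infusion and at the Day 56 visit", and Day 12 if that visit is held on site. It makes no exception for Day 56.
- Table 1 footnote f, which applies to the whole ECG row, says "to be obtained after 5 minutes of rest in the supine position and in triplicate at least 1-2 minutes apart".
- Section 7.1, for screening, says "12-Lead ECG (to be obtained in triplicate after 5 minutes of rest in the supine position".
- Section 7.16, for Day 56, says "12-Lead ECG (to be obtained in triplicate after 5 minutes of rest in the sitting position", and then points to Section 6.6.

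The Day 0, Day 12 and Day 28 visit lists (Sections 7.2, 7.7 and 7.11) state no posture and refer to Section 6.6.

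For the analysis, Section 12.5 averages each triplicate and then states that "change from baseline to each post-dose time point will be calculated". It adds shift tables from pre-dose to each post-dose time point and counts of QTcF above 450 at each time point. Section 4.2 includes ECGs in the primary safety measure.

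**The concern.** A change from baseline is interpretable only if both readings are taken under the same conditions. Section 7.16 asks for one posture at Day 56, while the only available baseline was taken in another. The line contradicts the section it cites, so a site can follow the protocol and still record the ECG either way.

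What is at stake is the last ECG of the study. Table 1 schedules none at Day 84 or Day 112, so Day 56 is the only look at whether an ECG change seen during dosing has persisted or resolved. The study is open-label with no control group, so nothing shows what the sitting-minus-supine difference would have been without drug. Posture is also fixed when the trace is recorded. Section 6.6 does not list it among the parameters collected, so an analysis plan could not recover it later from the ECG data the protocol asks for.

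**Working it through.** The protocol states no figure that bears on this point, so the check is a comparison of passages.

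**Step 1: posture at each scheduled ECG (current protocol text).**

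| ECG | Timing | Posture in the visit list | Posture in Section 6.6 and footnote f |
|---|---|---|---|
| Screening | before dosing | supine (7.1) | supine |
| Day 0 | 5 minutes after infusion ends | not stated (7.2) | supine |
| Day 12, on site only | between doses | not stated (7.7) | supine |
| Day 28 | 5 minutes after infusion ends | not stated (7.11) | supine |
| Day 56 | 56 − 28 = 28 days after the last scheduled dose | **sitting** (7.16) | **supine** |

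Day 56 is the only row in which the visit list and the general rule disagree. No reason for a different posture is given anywhere.

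**Step 2: which ECG is the baseline.** Section 12.5 does not name the ECG baseline visit. The Day 0 ECG follows the infusion, so screening is the only pre-dose recording, and it is supine.

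**Step 3: what the Section 12.5 summaries then measure at Day 56.**

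- Site follows Section 6.6 or footnote f: supine minus supine, the intended contrast.
- Site follows Section 7.16: sitting minus supine, that is, drug effect plus posture effect.
- Sites differ: a cohort mean mixing the two contrasts, in proportions the protocol provides no means of knowing. About 10 sites are planned (Section 4.1), with 8 subjects per cohort.

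Nothing in Section 12.5 adjusts for posture, and there is no concurrent control from which to estimate the effect.

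**Step 4: what is untouched.** At screening, Day 0, Day 12 and Day 28 no instruction conflicts with supine. The contrasts immediately after infusion, at Day 0 and Day 28, are therefore unaffected.

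**The case against.** The strongest reply is that Day 56 is already specified as supine twice, in Section 6.6 and in Table 1 footnote f, and that the Section 7.16 line sends the reader to Section 6.6. Sites need Section 6.6 anyway, because the Day 0, 12 and 28 lists give no posture. On this view the word is a slip that most sites would resolve correctly. That stands as far as it goes: the bias arises only where Section 7.16 is followed. It does not remove the contradiction. Section 7.16 is an operative instruction for that visit, and it states a posture explicitly.

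The limits on impact also stand. The ECG analysis consists of summary statistics, shift tables and counts. None of the stopping rules in Section 8.4 turns on a numeric ECG criterion. The synopsis endpoint table lists only AEs and laboratory tests under the primary objective, although Section 4.2 does include ECGs.

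Two stronger readings are tempting, and the documents support neither.

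A reader might infer that every subject, 16 to 24 in all, is shifted in the same direction. That would require every site to follow Section 7.16 over the two supine instructions, and a uniform posture response that the documents do not describe.

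A reader might also put a size on the bias. Suppose sitting raises heart rate from 70 to 75 or 80 bpm while QTcF stays at 420 msec. With QT = 420 × RR^(1/3) and RR = 60 / heart rate, QT is 399.0, 389.9 and 381.6 msec, a change of −9.1 or −17.4 msec. All of these inputs are assumptions from outside the protocol. The figures concern uncorrected QT only: QTcF is held constant by construction, so they say nothing about the QTcF above 450 count, the one numeric ECG threshold in the plan.

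**Conclusion.** The contradiction is real and is in the current text. Section 7.16 conflicts with Section 6.6 and with Table 1 footnote f, and it departs from the posture of the only pre-dose ECG. The consequence is conditional: where Section 7.16 is followed, the Day 56 change from baseline and shift table confound posture with drug effect, and posture may vary by site.

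The size of any distortion cannot be derived from the documents, and none is claimed here. The point is confined to one visit of a descriptive analysis. It is worth correcting because that visit has the only ECG after the Day 28 post-infusion recording, there is no control arm, and the correction is very cheap.

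The conclusion rests on one inference, that screening serves as the ECG baseline. The protocol does not say so, but no other pre-dose ECG is scheduled.

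**What to change.** In Section 7.16, change sitting to supine so that it agrees with Section 6.6, Table 1 footnote f and Section 7.1, and notify the sites.

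For Day 56 ECGs already recorded, ask each site which posture was used and flag any taken sitting. Present the Day 56 change from baseline with and without the flagged recordings. Dropping them outright is not needed and could discard the only ECG those subjects have after Day 28.

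The cost is a one-word correction with the usual IRB submission under Section 15, plus a short query to sites. No procedure or visit is added.

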### 7.18 Follow-up Day 112 (End-of-Study) or Early Termination Visit

On Day 112 ( $\pm$  5 days), subjects are to return to the clinic and the following procedures are to be performed:

- Complete physical exam ([Section 6.3](#))
- Vital sign measurements (after 5 minutes of rest; sitting blood pressure, heart rate, respiratory rate, oral temperature); abnormal results to be repeated after 5 minutes of rest ([Section 6.5](#))
- Clinical safety laboratory tests (hematology, serum chemistry panel, urinalysis) ([Section 6.7](#))
- Pregnancy test (Section 6.7)
- Serum tetanus antibody and VZV antibody testing if required. See [Section 6.7.3](#) for additional information.
- Immunogenicity sample collection (Section 6.7)
- PDAI Score ([Section 6.4](#))
- PD sample collection (Section 6.7)
  - IgG, IgG subtypes (IgG1-4), IgA, IgM
  - CIC
  - Anti-Dsg (1 and 3) antibody titer
  - C3
  - AECA
  - RNAseq
  - Urine IgG
  - Exploratory pemphigus immune response biomarkers
- Photography ([Section 6.11](#))
- Concomitant medication assessment ([Section 6.9](#))
- AE assessment ([Section 6.10](#))

## 8 REMOVING SUBJECTS FROM STUDY

Every reasonable effort will be made to keep the subject in the study; however, if a subject is withdrawn from the study, every effort will be made by the Investigator to complete and report the reasons for withdrawal as thoroughly as possible. The reason(s) for termination must be clearly documented on the appropriate page of the eCRF. Once a subject discontinues from the study for any reason, every effort will be made to collect all clinical and laboratory data as scheduled for the Early Termination Visit (See [Table 1](#)). A termination eCRF must be completed for all enrolled subjects.

### 8.1 Subject Withdrawal

A subject's participation in the study may be prematurely discontinued for any of the following reasons:

1. The subject wishes to withdraw from the study.
2. Request by a regulatory agency (e.g., Institutional Review Board).
3. Subject experiences a significant or intolerable AE.
4. The subject experiences a significant adverse change in vital signs, PE findings, or a clinical laboratory parameter.
5. The subject has a need for a concomitant medication that is not permitted by the study protocol.
6. The subject experiences generalized impairment or mental incompetence that would result in the subject being unable to understand his or her participation in the study.
7. If, in the Investigator's medical judgment, further participation would be injurious to the health and well-being of the subject, or is not in the best interest of the subject.
8. Administrative reasons, such as subject non-compliance or a major protocol violation.

Subjects who are withdrawn from this study due to an AE determined to be related to study drug are to be followed until there is either:

- Resolution or stabilization of the AE determined to be related
- The subject is lost to follow-up
- The event is otherwise explained

If there is a persistent AE contributing to discontinuation that is determined to be related to SYNT001, subjects must be followed with appropriate medical management until resolution or stabilization.

A reasonable effort should be made to contact any subject lost to follow-up during the study to complete assessments and retrieve any outstanding data. If the subjects are unreachable by telephone after three (3) attempts, the minimum of a registered letter should be sent requesting that contact be made with the Investigator to report survival information.

